14.2 Step 1: coronary artery bypass surgery and gene therapy period

During the gene therapy period (7 days), the subjects will be hospitalized for treatment.

1) Clinical evaluation

Symptoms of ischemic heart disease and physical examination: vital signs, auscultation findings, and other clinical examination findings. Canadian angina class, New York heart association functional classification

2) Laboratory test

(Note: The test results for anti-HGF antibodies and HGF protein in blood will be recorded in the case report form after the completion of the 24-week follow-up period.)

1. General Blood Tests

- Common Tests
 - Days 0, 1, 2, 5, and 7: CBC with differential count

- Days 1 and 7: ESR
- Additional tests by study group: None

2. General Chemistry Tests

- Days 1, 2, 5, and 7: Admission battery with electrolytes, lipid battery
- Days 1 and 7: CRP

3. Urinalysis: performed on Days 1, 5, and 7

4. ECG: follow-up on Days 0, 1, 2, 5, and 7

5. Cardiac Enzymes (CK/CK-MB, LDH, Troponin I): performed on Days 0, 1, 2, 5, and 7

6. Chest X-ray: performed on Days 0, 1, 2, 5, and 7

7. Echocardiography (TTE): performed on Day 7

8. Holter Monitoring: performed on Day 7

9. Blood Sampling for HGF Protein: performed on Day 7

(Tests on the day of surgery [Day 0] should be performed prior to the procedure.)

3) Intensive care and monitoring

1. Day of Surgery (POD#0 DAY): After surgery, the patient is transferred to the intensive care unit (ICU) with ventilatory support. The amount of bleeding is monitored through chest tubes inserted into the pericardium, mediastinum, and left and right pleural cavities in the operating room. Reoperation is considered in cases of significant bleeding (e.g., 500cc within 1 hour, 400cc/hr over 2 hours, or 300cc/hr over 3 hours). Continuous monitoring of systemic arterial pressure and pulmonary arterial pressure is performed. Medications (inotropics or vasodilators) and fluids are administered as needed based on hemodynamic status. Transient arrhythmias such as ventricular arrhythmias or atrial fibrillation are monitored via 24-hour ECG, and antiarrhythmic therapy (e.g., amiodarone) is administered if necessary. The patient's level of consciousness is assessed after awakening from anesthesia.
2. POD#1 DAY: If there is no bleeding and the hemodynamic status is stable, the ventilator is removed. Intravenous vasodilators are switched to oral medications. Continuous monitoring of systemic and pulmonary arterial pressure and ECG continues. Once hemodynamic stability is confirmed, the patient is transferred to the general ward and monitored with a 24-hour ECG.
3. POD#2 DAY: Under 24-hour ECG monitoring, the patient begins light physical activity in the ward. Chest tubes are removed if daily drainage is less than 1cc per kg of body weight.
4. POD#3 ~ 6 DAY: While continuing 24-hour ECG monitoring, physical activity is gradually increased in the ward. The patient is observed for allergic reactions possibly related to gene therapy, such as skin rashes, angioedema, or bronchospasm.
5. POD#7 DAY: Holter monitoring is performed, and transthoracic echocardiography is conducted to evaluate cardiac function. If no abnormalities are found, discharge is considered.

14.3 Step 2: follow-up period

1) Follow-Up Assessment Schedule

A total of 24 weeks of follow-up evaluations will be conducted. Based on the day of surgery (Day 0), follow-up visits will occur at Weeks 2, 4, 8, 12, and 24. The visit window will be ± 4 days for Weeks 2 and 4, and ± 7 days for Weeks 8, 12, and 24.

2) Clinical Evaluation

1. Assessment of medication status
2. Evaluation of symptoms and physical examination related to ischemic heart disease: vital signs, auscultation findings, and other clinical signs; Canadian Cardiovascular Society (CCS) classification; New York Heart Association (NYHA) functional classification

3) Laboratory tests

(Note: The results of anti-HGF antibody and HGF protein levels in blood will be recorded in the case report form after completion of the Week 24 follow-up period.)

1. Complete Blood Count: CBC with differential count, ESR: Performed at Weeks 2, 4, 12, and 24.
2. General Chemistry Tests: Admission battery with electrolytes, lipid battery, CRP: Performed at Weeks 2, 4, 12, and 24.
3. Urinalysis: Performed at Weeks 2, 4, 12, and 24.
4. Cardiac Enzymes: CK, CK-MB, LDH, Troponin I: Performed at Weeks 2, 4, 12, and 24.
5. Chest X-ray: Performed at Weeks 2, 4, 12, and 24.
6. ECG: Performed at Weeks 2, 4, 8, 12, and 24.
7. Echocardiography (TTE): Performed at Weeks 12 and 24.
8. Coronary Angiography (CAG): Performed at Week 24.
9. Myocardial SPECT and Cardiac MRI: Performed at Weeks 12 and 24.
10. Blood Sampling for Anti-HGF Antibody: Performed at Weeks 2, 4, and 24.
11. Blood Sampling for HGF Protein: Performed at Weeks 2, 4, 8, 12, and 24. If two consecutive results are negative, testing will be discontinued, and results will be considered negative.
12. Holter Monitoring: Performed at Weeks 2, 4, 12, and 24.
13. Fundus Photography: Performed at Weeks 2, 4, 12, and 24.
14. Tumor Marker Tests (CEA, PSA, alpha-fetoprotein, CA19-9, CA125) and Fecal Occult Blood Test: Performed at Weeks 12 and 24.

14.4 Step 3: long-term follow-up

Long-term follow-up will be conducted to monitor for serious adverse events such as cancer occurrence and survival status at 1, 2, 3, 4, and 5 years after administration of VM202RY. If in-person visits are not possible, follow-up may be conducted via telephone. The timing of each visit should occur at one-year intervals from the date of investigational drug administration, within a \pm 30-day window. The sponsor shall report the annual telephone follow-up results to the Ministry of Food and Drug Safety (MFDS) each year. Additionally, any serious adverse events related to the investigational drug that occur during this period must be promptly reported to the MFDS.

15. Adverse events and precautions for use of VM202RY

Various methods have been attempted to deliver the therapeutic gene to the target myocardium, but none have yet secured a definitive advantage. Therefore, this research team aims to evaluate the safety of VM202RY by directly injecting it into the myocardium after performing standard coronary artery bypass graft (CABG) surgery. The target patients are those who are candidates for CABG and are expected to benefit most from gene therapy—specifically those with reversible myocardial regions or areas with incomplete reperfusion due to issues with the target coronary artery or graft vessels during surgery.

To date, no adverse effects have been reported in preclinical or clinical studies indicating that injection of the hepatocyte growth factor gene into the myocardium—or similar gene therapies—has a direct negative impact on CABG procedures

16. Discontinuation and withdrawal of subjects from the clinical trial

16.1 Criteria for discontinuation and treatment/safety measures

Subjects who have agreed to participate in this clinical trial may be withdrawn from the study under the following circumstances:

1. If it is newly determined that the subject does not meet the inclusion/exclusion criteria
2. If the subject exhibits hypersensitivity reactions to the investigational product
3. If it becomes difficult to continue the trial due to evident adverse effects
4. If clinical deterioration or death occurs, making it difficult to proceed with the trial
5. If, in the investigator's judgment, continued participation in the trial may be harmful to the subject

However, if any of the above conditions occur post-surgery, and it is difficult to distinguish them from the natural progression of the disease, the subject may continue to be included in the study for ongoing observation, and appropriate measures will be taken as needed.

16.2 Criteria for subject withdrawal and treatment/safety measures

Subjects who have agreed to participate in this clinical trial may be withdrawn from the study under the following circumstances:

- 1) If it is newly determined that the subject does not meet the inclusion/exclusion criteria
- 2) If recurrent myocardial infarction occurs before the initiation of coronary artery bypass grafting (CABG) and intramyocardial gene therapy
- 3) If clinical deterioration or death occurs before the initiation of CABG and intramyocardial gene therapy
- 4) If, during the treatment or follow-up period, the subject takes medications or consumes excessive alcohol that may affect the clinical outcome evaluation
- 5) If the subject no longer wishes to continue treatment
- 6) If the subject does not comply with the instructions of the principal investigator or sub-investigator, or misses two or more scheduled follow-up visits
- 7) If, in the judgment of the investigator, continued participation in the clinical trial may be harmful to the subject

If a subject is withdrawn or discontinues participation during the clinical trial, the investigator shall make every effort to provide standard clinical care. The sponsor shall provide compensation in accordance with the subject compensation policy, if applicable.

All such situations must be documented in the subject's Case Report Form (CRF) and source documents. For subjects who discontinue early, the reason for early termination must be recorded in the clinical trial completion section of the CRF, and tests and follow-up visits scheduled for the final visit should be conducted as much as possible.

Even if a subject discontinues early, previously collected test results may still be used for analysis, and additional subjects may be enrolled in the trial to compensate for those who drop out.

17. Statistical analysis methods

17.1 Evaluable subjects

In this study, all subjects who participated and received at least one dose of the investigational drug (including those who dropped out) will be included in the analysis.

17.2 Handling of data from subjects who drop out

If a subject drops out during the study, the analysis will be conducted based only on the data obtained up to the point of dropout.

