17.3 Primary endpoint: safety

17.3.1 Safety evaluation population

Subjects who have been administered the investigational drug will be included, regardless of protocol violations or adherence to visit schedules. This clinical trial is designed to evaluate safety over a 6-month period.

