18.5 Follow-up management of adverse drug reactions

The principal investigator or responsible person must observe and document all adverse drug reactions related or possibly related to the investigational product that occur during the clinical trial period (from drug administration through follow-up). Monitoring should continue until the adverse reaction returns to baseline or normal levels, the investigator determines the reaction has resolved, or further observation is deemed unnecessary. Upon resolution of the adverse drug reaction, it must be reported to the MFDS. Whenever possible, the reason for discontinuation, treatment provided, and other course details should be investigated. If the subject does not visit in person, follow-up should be conducted via phone or mail.

19. Quality control and assurance of the clinical trial

Before the start of the trial, ViroMed staff, investigators, trial coordinators, and monitors will hold an Investigator's Meeting or Initiation Visit. Detailed discussions will be conducted on the protocol, trial procedures, case report form completion, and specimen collection methods.

Evaluators will receive appropriate training on assessment methods and tools during the Investigator's Meeting or Initiation Visit. Evaluators unable to attend prior training or joining later in the trial will receive training from the investigator or a designated person.

CMIC Korea and ViroMed will provide the trial sites with relevant guideline documents, and monitors will conduct monitoring according to those guidelines. Periodic site visits will be performed to compare source documents with case report forms and verify that the investigator conducts the trial according to the protocol and regulations, ensuring quality control. Communication with site investigators will also occur via mail, phone, and fax. After retrieving case report forms for subjects who have completed the trial, data review will be conducted.

All data will be verified by double data entry into the database. All source documents will be reviewed and corrections made to data entries. After data entry completion, logical checks will be run to identify inconsistent dates or lab test results outside normal ranges. All necessary database corrections will be documented in appendices or audit trails.

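### The dropout rule in section 17.2 states no exception for safety, so data collected after a dosed subject withdraws may fall outside the 6-month safety analysis

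*Combined protocol and SAP*

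**What the plan says.** Section 17.2 is a single sentence. If a subject drops out, "the analysis will be conducted based only on the data obtained up to the point of dropout". It stands directly after the definition of evaluable subjects and ahead of both the safety and the efficacy subsections, so on its face it covers both.

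Other sections bear on the same data:

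- Section 17.1: every subject who "received at least one dose of the investigational drug (including those who dropped out) will be included in the analysis".
- Section 17.3.1: the safety population is everyone dosed, whatever their visit adherence, and "This clinical trial is designed to evaluate safety over a 6-month period".
- Section 17.3.3, item 3: all adverse events and their severity are to be presented by dose group.
- Section 16.2: after early discontinuation, "tests and follow-up visits scheduled for the final visit should be conducted as much as possible". On use of the data it adds only that "previously collected test results may still be used for analysis".
- Section 16.1, closing paragraph: where a discontinuation ground arises after surgery and is hard to separate from disease progression, "the subject may continue to be included in the study for ongoing observation".
- Section 18.5: the investigator follows "all adverse drug reactions related or possibly related to the investigational product". "Monitoring should continue until the adverse reaction returns to baseline or normal levels", or until the investigator judges the reaction resolved or further observation unnecessary. Phone or mail is used if the subject does not attend.

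**The concern.** The product is given once, during surgery. A subject who later leaves the study has received the whole dose, so withdrawal does not reduce exposure and gives no reason to stop counting safety findings. Several discontinuation grounds in 16.1 (hypersensitivity, evident adverse effects, clinical deterioration) are themselves safety-related, so withdrawal may coincide with the period of most interest.

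The protocol asks for data after that point, yet the analysis rule, taken at its word, does not use them. Safety over 6 months is the primary endpoint and the groups hold three or four subjects. A single finding left out of the tables can therefore change what a dose group appears to show.

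**Working it through.** **1. Group size.** Section 11.4 plans 3 completers per group, and 3 groups × 3 = 9 agrees with the synopsis. One dropout who is replaced gives 3 + 1 = 4 dosed subjects in that group.

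**2. What is collected after withdrawal, and whether 17.2 lets it in.**

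| Data after withdrawal | Asked for in | Literal 17.2 | If dropout includes the 16.2 final visit |
|---|---|---|---|
| Final-visit tests | 16.2 | not analysed | analysed |
| Outcome of a reaction that began before withdrawal | 18.5 | onset counted, later course not | the same, for anything after the final visit |
| New event found later, e.g. by phone | 18.5, if related or possibly related | not analysed | not analysed, if after the final visit |

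Events before withdrawal are counted on either reading, through 17.1 and 17.3.1.

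**3. Tests that come late.** The schedule of evaluations and section 14.3 place tumour markers, fecal occult blood and cardiac MRI after dosing only at Weeks 12 and 24. Section 17.3.3 uses MRI to look for intramyocardial hemangioma. For a subject withdrawn before the Week 12 assessment, the number of scheduled post-dose results before withdrawal is 0. The 16.2 final-visit set would be the only planned one. Under a literal 17.2 it is collected and not analysed.

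**4. Effect of one omitted event.** Exact (Clopper–Pearson) 95% intervals, the plan itself calling for incidence with a 95% interval:

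- 4 dosed, event counted: 1/4 = 25%, interval 0.6% to 80.6%.
- 4 dosed, event omitted: 0/4, upper limit 1 − 0.025^(1/4) = 60.2%.
- 3 dosed: 1/3, interval 0.8% to 90.6%, against 0/3, upper limit 70.8%.

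The intervals overlap almost entirely. What changes is whether the group shows an event at all.

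**5. How often a subject might leave before Week 12.** The documents give no dropout rate. Assume a 24-week rate d of 5%, 10% or 20%, spread evenly. The chance that at least one of 9 leaves before Week 12 is 1 − (1 − d × 12/24)^9:

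- d = 5%: 1 − 0.975^9 = 0.204
- d = 10%: 1 − 0.95^9 = 0.370
- d = 20%: 1 − 0.90^9 = 0.613

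This is the chance that the question arises, not the chance that an event is lost.

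**6. Side point: the DLT tally.** The escalation steps in 17.3.3 have branches for 3 and for 6 subjects only, while dropouts are replaced over 24 weeks. Suppose one of the first 3 at a dose is lost before Week 4 with no DLT seen, and let q be an assumed DLT rate. If that subject counts as DLT-free, P(escalate) = (1 − q)² + 2q(1− q)⁴. If replaced, it is (1 − q)³ + 3q(1 − q)⁵.

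| q | Counted DLT-free | Replaced | Difference |
|---|---|---|---|
| 10% | 0.941 | 0.906 | 0.035 |
| 20% | 0.804 | 0.709 | 0.095 |
| 30% | 0.634 | 0.494 | 0.140 |

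These figures are conditional on such a loss occurring.

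**The case against.** The strongest reply is that 17.2 is an ordinary no-imputation rule: use what was obtained and carry nothing forward. On a related reading, 16.2 mentions the final-visit tests together with completing the trial-completion section of the CRF, so those tests can be taken as the closing act of dropout and hence as data obtained up to it. If so, the conflict with 16.2 disappears, and with it the statement that no late-test result is analysed. That is a reasonable reading. But the point of dropout is nowhere defined, and the reference in 16.2 to previously collected results leans the other way.

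Second, 17.3.3 promises that all adverse events will be presented, and sections 17.3.3 and 18 require all of them to be recorded. As specific provisions for the primary endpoint they could be held to override the general sentence in 17.2. The plan does not say which prevails.

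Third, 18.5 adds less than it seems to. It is a monitoring and reporting duty, it does not name dropouts, and it mostly supplies the outcome of reactions already counted. The 1/4 against 0/4 comparison therefore needs a new event found after withdrawal. That stands.

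Fourth, a reader might infer that a late cancer in a dropout would go unnoticed. The documents do not support that. Survival and cancer are followed at Years 1 to 5, by telephone if need be, with yearly reports to the regulator. The stop on escalation for attributable cancer or proliferative retinopathy has no dropout cut-off, and fundus photography is also scheduled at Weeks 2 and 4. The long-term follow-up does not close the gap in the analysis, however, because 13.3 manages it separately from the trial results.

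**Conclusion.** The concern holds as a conflict on the literal wording. Section 17.2 stops the analysis at an undefined point and states no exception for safety, while other sections set a 6-month safety evaluation of everyone dosed and ask for data after withdrawal. The milder readings narrow this, but neither is established by the text.

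On the literal reading, a subject withdrawn before Week 12 has no analysed post-dose tumour-marker, fecal occult blood or MRI result. One new event found after withdrawal could be a group's only event (1/4 against 0/4). How often this would arise depends on a dropout rate that the documents do not give.

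A reader might go further and infer that withdrawn subjects, or their earlier events, vanish from the safety analysis. Sections 17.1 and 17.3.1 rule that out. Nor do the documents show that escalation decisions would go wrong. The DLT tally is missing detail, its figures rest on assumed rates and a conditional event, and it is a minor clarification only.

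**What to change.** Amend 17.2 so that all safety data collected on a dosed subject up to Week 24 enter the 6-month safety analysis, including 16.2 final-visit tests and 18.5 follow-up obtained after withdrawal. Define the point of dropout. The cut-off may stay for efficacy.

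As a minor clarification, reconcile the replacement passages (synopsis, 11.4, 13.4.6, 16.2) with the tally in 17.3.3. State, in line with 17.3.1, that a dosed subject's observed DLT stays in the count. The sponsor should also say how early losses without a DLT, and replacements, are counted.

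The cost is wording. No visit or test is added, since 16.2 and 18.5 already ask for these data, and the withdrawal grounds are unchanged. The drawback is that post-withdrawal data will be incomplete for subjects who refuse contact, so the safety tables should show how long each subject was actually followed.

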17.3 Primary endpoint: safety

17.3.1 Safety evaluation population

Subjects who have been administered the investigational drug will be included, regardless of protocol violations or adherence to visit schedules. This clinical trial is designed to evaluate safety over a 6-month period.

17.3.2 Safety evaluation items

- 1) Dose Limiting Toxicity (DLT) assessment
- 2) Tolerated Dose (TD) assessment
- 3) Adverse reactions, vital signs, physical examination, and laboratory test results
- 4) Major Adverse Cardiovascular Events (MACE)
- 5) Safety assessment of VM202RY intramuscular injection

17.3.3 Safety evaluation methods and criteria

1) DLT (Dose Limiting Toxicity)

Dose Limiting Toxicity (DLT) is evaluated from the first day of investigational drug administration up to 4 weeks post-administration. DLT is defined as adverse reactions of Grade 3 or higher according to the WHO Toxicity Scale, or severe adverse reactions classified as Grade 3 by Spilker's three-tier classification method, excluding adverse reactions associated with coronary artery bypass grafting (CABG).

Adverse reactions specific to CABG caused by the surgery itself are excluded from the DLT evaluation.

1. Blood test findings (in cases recovered without complications)
 - (1) Hemoglobin: 8-17
 - (2) WBC: 4-25
 - (3) Platelet: 50-550
 - (4) Bilirubin: 0.3-10.6
 - (5) GOT/GPT: 9-125/8-350

- (6) Alk. Phosphatase: 35-180
- (7) BUN/Cr: it depends on the patient's preoperative kidney function
- 2. Reoperation due to bleeding: occurs in 5-10% of cases.
- 3. Fever: A persistent fever above 39°C is rare unless pulmonary complications or infections occur. Therefore, a fever above 39°C lasting more than 24 hours is considered outside the range of common complications.
- 4. Infection: Mediastinitis occurs in 2-3% of cases.
- 5. Arrhythmia: Atrial fibrillation occurs in 20-30% of cases. Transient premature ventricular contractions (PVCs) are common, but the occurrence of multifocal PVCs is considered abnormal. Ventricular tachycardia and fibrillation may occur due to postoperative bleeding, myocardial dysfunction, or reperfusion injury in chronically ischemic areas. If these are clearly related to surgery, such as bleeding from the graft or cardiac tamponade, they are considered surgical complications. However, unexplained ventricular arrhythmias can occasionally occur. Recurrent ventricular arrhythmias are uncommon in patients discharged after surgery. If the patient had recurrent ventricular arrhythmias before surgery with a consistent pattern and interval, these are not considered caused by gene therapy, but follow-up with Holter monitoring is needed to track any changes.
- 6. Allergic reactions: Occasionally, skin rash or bronchospasm occur after contrast agent use for preoperative imaging tests (coronary angiography, CT, MRI). Skin rash, bronchospasm, or anaphylactic shock can also occur due to blood transfusion reactions before or after surgery. These reactions typically occur immediately after administration of the causative agent and can usually be distinguished from reactions caused by gene therapy. However, since gene therapy is administered during surgery, which often involves transfusions, distinguishing the cause can be difficult. It is important to identify parameters such as rash occurrence or increased airway resistance on the ventilator immediately after surgery or during surgery—especially before and after gene injection—to clarify causality.

Assessment of adverse reactions related to coronary artery bypass grafting (CABG)

- 1. If continuous bleeding occurs after surgery (500 cc in the first hour, 400 cc/hr for the first 2 hours, 300 cc/hr for the first 3 hours) requiring re-thoracotomy, and surgical findings reveal that the bleeding is not from the gene injection site but rather from side branches of the graft, anastomosis sites, or diffuse bleeding at the wound caused by antiplatelet agents used to prevent graft occlusion, this is considered a surgical complication rather than an adverse reaction to gene therapy.
- 2. In cases of postoperative mediastinitis, only if the sterile distilled water used to dissolve the gene tests positive in culture for the same pathogen isolated from the patient is the complication considered related to gene injection. Otherwise, it is determined to be an infection related to CABG.
- 3. If complications such as skin rash or bronchospasm occur after blood transfusion, antibiotic injections, or contrast-enhanced tests following surgery, these will be evaluated by an allergy specialist to determine any association with gene therapy. If no causal relationship with the administered gene is found, the reactions will be regarded as general adverse reactions related to CABG.

4. Other adverse reactions characteristic of CABG mentioned above will be classified as surgery-related complications.

Reactions due to surgery listed under WHO toxicity scale items

According to the WHO Toxicity Scale, toxicities of Grade 3 or higher are generally considered dose-limiting. However, since this clinical trial includes surgery, the following reactions caused by surgery are excluded from the DLT (Dose-Limiting Toxicity) evaluation:

Adverse events caused by coronary artery bypass graft (CABG) surgery are excluded from the DLT evaluation.

1. Hematology

- Hemoglobin: Decrease due to surgical bleeding that recovers with transfusion.
- Hemorrhage: Common post-operative complication. However, persistent bleeding at the gene injection site should result in discontinuation of dose escalation.

2. Gastrointestinal

- Bilirubin: Elevation up to 10.6 due to intra-body retention of hematoma after surgery is considered a normal response.
- GOT/GPT (AST/ALT): Levels up to 125/350 are excluded if attributable to transfusion or myocardial ischemia.

3. Renal / Bladder

- Proteinuria: If caused by pre-existing diabetes or renal failure.
- Hematuria: If caused by trauma during Foley catheter insertion.

4. Pulmonology: Findings due to decreased cardiac function.

5. Fever: Fever above 39°C lasting less than 24 hours (unless associated with pulmonary complications or infection).

6. Allergic Reactions: When the cause is clearly identified, such as contrast agents, antibiotics, or blood transfusion.

7. Cardiac

- Rhythm: Arrhythmias are unavoidable due to surgical dissection of the myocardium. While ventricular arrhythmias may occur due to reperfusion of chronically ischemic areas, establishing a direct association with gene injection is difficult. However, in the interest of patient safety, WHO Grade 3 criteria will be followed and dose escalation will be discontinued.
- Cardiac Function: Most patients have impaired cardiac function due to the nature of cardiac surgery; thus, excluded from DLT evaluation.
- Pericarditis: Most cases involve post-operative accumulation of blood or fluid in the pericardial space. Surgery may be necessary, but dose escalation will be discontinued only if bleeding is confirmed at the gene injection site.

2) TD (tolerated dose) evaluation

Subjects are enrolled sequentially, starting from Step 1, to determine the tolerated dose as follows:

1. Step 1: Three subjects are enrolled. DLT (Dose-Limiting Toxicity) is evaluated 4 weeks after the third subject is dosed.
 - 1-1. If no DLTs occur in any of the 3 subjects (0/3) → Proceed to Step 2 and enroll 3 more subjects (A)
 - 1-2. If DLT occurs in 1 out of 3 subjects (1/3) → Enroll 3 additional subjects at the same dose
 - 1-2-1. If no DLTs in the additional 3 subjects (1/6) → Proceed to Step 2, enroll 3 more subjects (A)
 - 1-2-2. If 1 additional DLT occurs among the 3 (2/6) → Stop dose escalation
 - 1-3. If DLT occurs in 2 out of 3 subjects (2/3) → Stop dose escalation
2. Step 2: Three subjects are enrolled. DLT is evaluated 4 weeks after the third subject is dosed.
 - 2-1. If no DLTs occur in all 3 subjects (0/3) → Proceed to Step 3, enroll 3 more subjects (B)
 - 2-2. If DLT occurs in 1 out of 3 subjects (1/3) → Enroll 3 additional subjects at the same dose
 - 2-2-1. If no DLTs in the additional 3 subjects (1/6) → Proceed to Step 3, enroll 3 more subjects (B)
 - 2-2-2. If 1 additional DLT occurs among the 3 (2/6) → Stop dose escalation (A)
 - 2-3. If DLT occurs in 2 out of 3 subjects (2/3) → Stop dose escalation (A)
3. Step 3: Three subjects are enrolled. DLT is evaluated 4 weeks after the third subject is dosed.
 - 3-1. If no DLTs occur in all 3 subjects (0/3) → End of clinical trial (C)
 - 3-2. If DLT occurs in 1 out of 3 subjects (1/3) → Enroll 3 additional subjects at the same dose
 - 3-2-1. If no DLTs in the additional 3 subjects (1/6) → End of clinical trial (C)
 - 3-2-2. If 1 additional DLT occurs among the 3 (2/6) → End of clinical trial (B)
 - 3-3. If DLT occurs in 2 out of 3 subjects (2/3) → End of clinical trial (B)

Tolerated dose

Condition	Tolerated dose
A + B + C	C
A + B	B

A	A
---	---

3) Adverse events and laboratory test values

An adverse event is defined as any symptom, sign, or disease that occurs or worsens during the clinical trial, regardless of its relationship to the investigational drug. It is the responsibility of the investigator and study staff to record all adverse events that occur during the clinical trial. Adverse events should be recorded using medical diagnostic terminology; if that is not possible, terms describing observed symptoms and signs reported by the subject should be documented.

All adverse events, clinical laboratory test results, and vital signs (blood pressure, temperature, pulse, respiration) of the study subjects will be summarized in tables and reviewed comprehensively to assess dose-dependent trends. All clinically significant abnormal laboratory results should be recorded in the adverse event section of the case report form (CRF), and the severity, course, and relationship to the investigational drug must also be documented.

As the number of subjects assigned per dose group in a Phase I clinical trial is small, the determination of normal or abnormal laboratory test results will be made on a per-subject basis. Statistical validation may be performed if necessary. In particular, adverse events that are anticipated or listed in the precautions for use must be closely monitored for changes, and if observed, should be tabulated by dose group for comparative analysis.

- ① Since the test subjects have not previously been exposed to the investigational substance, pre-treatment allergy and anaphylaxis testing methods are considered not meaningful. In addition, as the vector was manufactured using kanamycin instead of ampicillin, skin testing is also deemed unnecessary. Furthermore, as the investigational agent is an angiogenic substance, skin testing may potentially induce angiogenesis in the skin and is thus discouraged.
- ② Although the concentration of HGF in the blood is expected to be minimal following intramyocardial injection, due to concerns about retinal neovascularization, fundoscopy will be performed before surgery and during the follow-up period to assess potential retinal lesions.
- ③ Cardiac MRI will be used to monitor for the development of intramyocardial hemangiomas.
- ④ The occurrence of ventricular arrhythmia will be monitored via continuous ECG during hospitalization and regular ECG during the follow-up period.

All adverse events and their severity by dose group will be presented, and incidence rates along with 95% confidence intervals will be estimated. If feasible, Fisher's Exact Test will be used for comparisons.

Vital signs (blood pressure, temperature, pulse, respiration) will be summarized with descriptive statistics by group and visit to evaluate trends. Physical examination findings will identify abnormal findings before and after administration, presented by group. For laboratory tests (general hematology and chemistry), descriptive statistics will be provided by group and visit to observe trends. For urinalysis, changes from normal (pre-dose) to abnormal (post-dose) will be presented by group and visit to assess trends.

4) Major Adverse Cardiac Event (MACE)

In this study, MACE is defined as cardiac death, myocardial infarction, ventricular arrhythmia requiring treatment, or hospitalization for target vessel revascularization. Investigators must monitor and confirm the occurrence of MACE. Any MACE must be reported to the sponsor in accordance with serious adverse event reporting guidelines. Inter-group comparisons of MACE incidence will be analyzed using Fisher's Exact Test.

5) Safety assessment of VM202RY intramyocardial injection

The safety of VM202RY intramyocardial injection will be evaluated by monitoring for persistent bleeding, arrhythmia, and other complications. Investigators must closely observe subjects for these events following VM202RY administration. The incidence of persistent bleeding, arrhythmia, and other complications will be presented by treatment group, and inter-group comparisons will be performed using Fisher's Exact Test.

